STUDY PROTOCOL

NCT04606199

IRB ID: 19-27198

Examine the Effects of Meditation on Daily Psychological Stress Responses in Woman With a History of Child Adversity

Document date: November 4, 2021

Study design: The study uses a small micro-randomized trial design—a design that randomly assigns an intervention at each notification time point. In the proposed study, participants use the study app for 30 days and receive up to 3 notifications/day (morning, afternoon, evening). At each notification time point, participants first complete a brief ecological momentary assessment of their current psychological states (feeling stressed, positive/negative affect, stress appraisals, perseverative cognitions). Then, at each notification, each participant is randomized (50% probability) to either receive a brief mindfulness-based intervention (randomly selected from a pool of interventions) or no intervention. Thus, participants are randomized many times over the study (and each intervention is randomized many times to each person). Psychological states are again measured about 15 minutes after a notification to compare proximal (within 15 min) changes in intervention targets following an intervention vs. no intervention (proximal treatment effect).

Human Subjects Involvement, Characteristics, and Designs

I will recruit a new sample of adults, all of whom are women exposed to early life adversity. The rationale for my focus on this population is informed by the detrimental health effects of early life adversity, and by a lack of empirically-based non-pharmacological interventions to buffer or reverse risk pathways.

The study aims to develop an Ecological Momentary Mindfulness-based Intervention (EMMI) that targets maladaptive daily psychological stress responses. A micro-randomized trial will test target engagement and obtain qualitative acceptability/feasibility data during the development of the EMMI.

Inclusion criteria:

- 1) female
- 2) age 30-60
- 3) ≥2 Adverse Childhood Experiences
- 4) mild depressive symptoms (Patient Health Questionnaire ≥ 5)
- 5) having a smartphone

Exclusion criteria:

- 1) non-English speaker or unable to provide informed consent
- 2) current regular mindfulness practice (>20 min/week)

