- 3) major psychiatric condition that necessitates priority treatment or interferes with participation, including psychoti disorder, bipolar disorder, Post-Traumatic Stress Disorder (PTSD), substance abuse/dependence, major depression (also indicated by PHQ-9 ≥ 15), self-harm or suicidal ideation (also indicated by PHQ-9, item 9)
- 4) Medication use and psychotherapy treatment has not been stable over the past 3 months.

Sources of Materials

The data collected in this study will include responses on self-report questionnaires, a short (15-20 minutes) diagnostic interview, app-based ecological momentary assessments and interventions, and audio-recordings of qualitative feedback on acceptability and feasibility. All data will be used for research purposes only. All data will be entered into or collected in electronic form. App-based ecological momentary assessment and intervention data will only use de-identified study ID numbers. Electronic data will be stored on a private, password-protected, encrypted hard drive accessible only to the PI or trained, authorized study staff. Hard copy data will be kept in locked filing cabinets in a locked office. Identifying information will be stored separately from data.

Potential Risks

Psychological distress from self-report questionnaires, diagnostic interviews, ecological momentary assessment of psychological responses, or generally heightened distress: Participants may experience temporary emotional discomfort or stress from responding to questions about their mental and physical health, early life adversities, and current psychological states. Although it is not anticipated that this study will cause significant psychological distress, it is likely that recruitment and assessment procedures will identify participants with elevated levels of distress. Protection against the risk that significant distress, and possibly worsening of depressive symptoms, and, in some cases, self-harm or suicidal ideation is developed during the study is outlined below.

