Psychological distress from audio-recorded qualitative interview: Audio-recorded semi-structured interviews will obtain qualitative information on the acceptability and feasibility of the Ecological Momentary Mindfulness-based Intervention (e.g., satisfaction with each intervention component, preferred frequency/duration of assessment and intervention sessions, any challenges that participant encountered in using the app, and general feedback on app usability). Interviews carry a minimal risk for emotional discomfort and stress. Efforts will be taken to maintain the participant's comfort and study procedures will be stopped at the request of the participant.

Psychological distress from participation in the intervention: Participation in the Ecological Momentary Mindfulness-based Intervention (EMMI) includes short ecological momentary assessments (1-2 minutes/notification) and brief audio-guided mindfulness-based interventions. Previous studies of mindfulness interventions, including those recruiting individuals with early life adversity and trauma, demonstrated reduced distress (depression and anxiety), enhanced coping and mood, and improved quality of life. Thus, the EMMI carries minimal risk for emotional discomfort or stress.

Confidentiality: Participation in research may involve a loss of privacy, however information will be handled with the upmost confidentiality. One limit to confidentiality is if a participant is at imminent risk of harming herself (see more under Protection Against Risk).

Inconvenience: There may be some burden associated with filling out self-report questionnaires and completing repeated ecological momentary assessments and interventions in the flow of everyday life. However, participants will be provided with compensation for their time and effort.

ADEQUACY OF PROTECTION AGAINST RISKS

Recruitment and Informed Consent

Prior to study commencement, all procedures will be approved by the UCSF Committee on Human Research (CHR, the equivalent to IRB). Potential participants will be recruited using methods my mentors, advisors, and I have found successful in previous research with participants with high exposure to early life adversity.

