There is strong conceptual basis to predict the benefit of a mindfulness-based ecological momentary intervention, including for participants with early life adversity. The minimal risks participants may experience in this study are reasonable in relation to anticipated benefits. Participants may experience improved psychological responding to daily stressors, improved mental and physical symptoms, as well as improved physiological markers as a result of daily mindfulness practices that are incorporated into everyday life. In the long-term, there are substantial benefits to be gained by developing and evaluating a mindfulness-based ecological momentary intervention to improve daily psychological stress responses, and ultimately to reduce or reverse psychological risk pathways associated with early life adversity.

IMPORTANCE OF THE KNOWLEDGE TO BE GAINED

Despite evidence that early life adversity can have detrimental consequences for midlife mental and physical health, there is a paucity of mechanism-focused non-pharmacological interventions. As a result of the proposed study, we will learn more about the psychological mechanisms linking early life adversity with midlife health outcomes, which will inform intervention targets, and about the acceptability, feasibility, and adherence of a mindfulness-based ecological intervention. This research will provide the preliminary data needed to evaluate the intervention in an adequately powered study.

STATISTICAL ANALYSIS

Using the centered and weighted least square method, which has been recommended for the analysis of proximal treatment effects in micro-randomized trials, I will test proximal (within 15 min) target engagement (also termed “proximal treatment effect”) by comparing changes (from current states at notification to about 15 min later) in each primary intervention target (positive/negative affect, threat/challenge appraisal, perseverative cognition) after an intervention vs. no intervention.

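### Should the plan estimate each mindfulness item's effect separately, because items are drawn at random from a pool?

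*Combined protocol and SAP*

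**What the plan says.** The Study design section describes two random steps at each notification. The woman is assigned with 50% probability to a "brief mindfulness-based intervention (randomly selected from a pool of interventions) or no intervention". The same section says that "participants are randomized many times over the study (and each intervention is randomized many times to each person". She uses the app for 30 days, with up to 3 notifications a day.

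The Statistical Analysis section is one paragraph. It uses centered and weighted least squares to compare the change over about 15 minutes in "each primary intervention target (positive/negative affect, threat/challenge appraisal, perseverative cognition) after an intervention vs. no intervention". It contains no term for the item drawn and no exploratory model.

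The purpose is given under Human Subjects Involvement, Characteristics, and Designs: "A micro-randomized trial will test target engagement and obtain qualitative acceptability/feasibility data during the development of the EMMI". The section on the importance of the knowledge to be gained adds that the work will supply the "preliminary data needed to evaluate the intervention in an adequately powered study". Under Potential Risks, the interview topics include "satisfaction with each intervention component".

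**The concern.** The design randomizes items within each woman, and the analysis then ignores which item she received. In a trial run while the intervention is still being built, it is natural to ask which items move the targets. The pooled contrast cannot answer that, because very different patterns give the same average. With five equally likely items:

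- every item at 0.10 SD: average 0.10;
- two items at 0.25 and three at 0: (0.25 + 0.25) / 5 = 0.10;
- graded effects of 0.20, 0.15, 0.10, 0.05 and 0: 0.50 / 5 = 0.10.

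If a few items carried the whole effect, the later study could go ahead with items that do nothing. The planned interviews may touch on individual items, but satisfaction with an item is not evidence that it changes affect, appraisal or perseverative cognition. A by-item model would need no new participants or assessments, so leaving it out looks like an oversight.

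**Working it through.** **1. Does the planned contrast answer the stated question?** The stated quantitative purpose is target engagement. The contrast is any item versus none, randomized at each notification. Writing p_k for the chance that item k is drawn once a notification is assigned to intervention, it estimates the sum over k of p_k × (effect of item k versus none). This is a well-defined average effect of the package as delivered, and it is valid whether or not the items differ. The documents contain no aim, hypothesis or decision rule about individual items, so no planned conclusion lacks an analysis.

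**2. What would a by-item model deliver?** The plan has no figure to reproduce here: sample size, pool size K, selection probabilities, response rate, effect size and SD are not stated. The documents give only the following:

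- Notifications per woman: at most 30 × 3 = 90.
- Expected interventions per woman: 90 × 0.5 = 45.
- Expected deliveries per item per woman, with equal selection assumed: 45/K, which is 15 at K = 3, 9 at K = 5 and 4.5 at K = 10.

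Everything below is assumed: equal selection, 60% response, effects in units of the residual SD, independent residuals, and no variation between women in effect. With n women, the number of answered intervention notifications is n1 = n × 54 × 0.5, which is 405, 810 and 1,620 for 15, 30 and 60 women.

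*Precision.* SE pooled = √(2/n1) and SE item = √((K+1)/n1). The ratio is √((K+1)/2), which is 1.41, 1.73, 2.12 and 2.35 at K = 3, 5, 8 and 10. The 95% half-widths at K = 5 use t with n − 2 degrees of freedom (pooled) and n − K − 1 (item):

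| Women | Pooled | Item vs none |
|---|---|---|
| 15 | 0.15 | 0.28 |
| 30 | 0.10 | 0.18 |
| 60 | 0.07 | 0.12 |

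*Power to show that items differ.* Noncentrality = (n1/K) × Σ(effect − mean effect)², referred to a noncentral F with K − 1 and n − K + 1 degrees of freedom, at 5%. The sum of squares is:

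- two of five items at 0.25: 2 × 0.15² + 3 × 0.10² = 0.075;
- graded, five items: 0.10² + 0.05² + 0 + 0.05² + 0.10² = 0.025;
- two of ten items at 0.25: 2 × 0.20² + 8 × 0.05² = 0.100.

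For 30 women the noncentralities are 162 × 0.075 = 12.15, 162 × 0.025 = 4.05 and 81 × 0.100 = 8.1. They halve for 15 women and double for 60.

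| Pattern | 15 women | 30 women | 60 women |
|---|---|---|---|
| Two of five at 0.25 | 33% | 72% | 98% |
| Graded, five items | 13% | 27% | 57% |
| Two of ten at 0.25 | 11% | 32% | 74% |

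With 30 women and five items, varying response from 40% to 80% moves the two-item figure from 52% to 85% and the graded figure from 19% to 36%. Simulation of the five-item cases (1,500 runs each, person-clustered variance, F reference) gave 28% and 70% for the two-item pattern and 12% and 25% for the graded one, with 15 and 30 women. Real variation between women in effect would lower all of these.

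*Multiplicity.* If the five targets are scored separately, K = 5 gives 5 × 5 = 25 contrasts. Tested at 5% without adjustment and treated as independent, the chance of at least one false positive is 1 − 0.95^25 = 0.72, against 1 − 0.95^5 = 0.23 for the five pooled contrasts.

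**3. What follows?** The protocol describes itself thus: "The study uses a small micro-randomized trial design". If that means 15 to 30 women, a by-item model separates the items reliably only if the differences between them are stark, the pool is short and the sample is at the upper end.

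**The case for a change.** The strongest reply is that the trial belongs to the development stage, where estimates with honest intervals are useful even when tests are weak. Item randomization comes free with the design. Specifying one model in advance would limit selective reporting. If the app does not record which item was drawn, the information may be lost for good: Sources of Materials says "App-based ecological momentary assessment and intervention data will only use de-identified study ID numbers" but does not say whether the item is among those data.

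Part of this stands. The pooled contrast is indeed silent on differences between items, and a by-item model labelled exploratory would do no harm. Under the stark two-item pattern with 30 women, power of about 72% is respectable, and with 60 women it is 98%. Stating the pool size and selection probabilities, and recording the item drawn, would be sensible documentation.

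None of it turns the omission into an error. The favourable figures need an assumed sample size, an assumed short pool and an assumed sharp split between items. Nothing in the analysis text rules out an exploratory by-item analysis later, provided the draws are recorded. Picking the best-looking items from about 25 noisy estimates also carries a risk of its own. The later study is described as an evaluation of the intervention, which reads most naturally as the package that the pooled contrast addresses.

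**Conclusion.** The concern does not hold. Items are drawn at random and the analysis pools them, but the pooled contrast is valid and answers the only quantitative question the protocol poses. Omitting a by-item model introduces no bias and alters no planned conclusion, so the effect on the trial's stated result is nil. What remains is a preference for one more exploratory analysis, together with some unstated detail about the pool.

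The benefit of that analysis cannot be established from the documents. With 15 to 30 women it would have 13% to 27% power to detect graded differences among five items and 11% to 32% for two active items among ten, rising to 33% to 72% only under a stark five-item pattern. Those figures assume equal selection, 60% response, independent residuals and no variation between women in effect. The finding that there is no error does not depend on them. It rests on the match between the stated aim and the stated contrast.

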Identification of participants with heightened distress: The proposed study aims to develop and pilot test an intervention tailored for individuals who have been exposed to early life adversity. As such, the recruitment and assessment procedures will identify individuals who will have subclinical or higher depressive symptoms. Some of these participants may be experiencing particularly significant distress and require clinical services beyond what the intervention will be able to provide. Thus, major psychiatric conditions (as determined by a diagnostic interview and the 9-item Patient Health Questionnaire, PHQ-9), including current moderately severe depressive symptoms (PHQ-9 ≥ 15) and self-harm or suicidal ideation (e.g., participant endorsed item 9 on PHQ-9: "Thoughts that you would be better off dead or of hurting yourself in some way") are an exclusion criterion. [name] study and mentoring team will immediately intervene and make appropriate referral for community care for participants. The study team will closely monitor depressive symptom severity and suicidal ideation among enrolled participants via weekly administration of the PHQ-9. Participants are instructed to make immediate contact with study personnel with any issues, questions, or concerns regarding worsening symptoms. At the first assessment visit, regardless of their current expressions of distress, participants are provided study contact information as well as local therapeutic and crisis resources. All study staff will be trained to probe for suicidal thoughts, intent, and psychotic behavior. If there is any suspicion of suicide risk or if participant endorses item 9 on the PHQ-9, study staff will immediately contact [name] so that appropriate steps can be taken to ensure the safety of the participants. [name] is a clinical psychologist who has extensive experience in assessing suicidal ideation and treating depression. She is a licensed Psychologist in the State of California. [name] and her study team will follow a written protocol for assessing and responding to suicide risk. This includes the evaluation of risk factors (e.g., plan, intent, access to lethal means) and protective factors (e.g., social support). For imminent risk, study staff will call emergency services and remain with the participant until emergency services arrive. For low to medium risk, study staff will provide mental health resources or psychological referrals, if needed.

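### Do several equally ranked primary targets, tested one by one without a multiplicity rule, need an adjustment or a lead target in this pilot?

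*Combined protocol and SAP*

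**What the plan says.** The analysis plan is a single sentence under Statistical Analysis. The investigator writes "I will test proximal (within 15 min) target engagement", using centered and weighted least squares, by comparing the change from notification to about 15 minutes later in "each primary intervention target (positive/negative affect, threat/challenge appraisal, perseverative cognition) after an intervention vs. no intervention". It gives no significance level, lead target, order of testing, joint test, multiplicity adjustment or rule for combining results across targets, and it does not call the tests exploratory.

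The Study design paragraph lists the states measured at each notification as "feeling stressed, positive/negative affect, stress appraisals, perseverative cognitions". The first of these is not among the primary targets in the analysis sentence.

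The study's standing is described in three other places:

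- Human Subjects Involvement, Characteristics, and Designs: "A micro-randomized trial will test target engagement and obtain qualitative acceptability/feasibility data during the development of the EMMI".
- Protection Against Risk: "The proposed study aims to develop and pilot test an intervention tailored for individuals who have been exposed to early life adversity".
- Importance of the Knowledge to be Gained: "This research will provide the preliminary data needed to evaluate the intervention in an adequately powered study".

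**The concern.** Several outcomes share the label primary and each is to be tested, yet nothing says how a mixed set of results would be read. A reader cannot tell whether one significant target would be reported as target engagement or as one estimate among several. The number of tests is also open: positive and negative affect, or threat and challenge appraisal, might be separate scores or combined.

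The apparent stake is what is carried into the next study. The section on the importance of the knowledge says that what is learned about mechanisms is something "which will inform intervention targets, and about the acceptability, feasibility, and adherence of a mindfulness-based ecological intervention". If the target with the smallest p-value were simply picked as the engaged one, a chance finding could shape the later trial. With three to five looks, a chance finding is clearly more likely than the nominal 5%.

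**Working it through.** **Inputs.** The documents state no significance level, power, sample size or family-wise error rate, so there is no figure of the plan's own to reproduce.

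- Number of tests k: 3 if each slash pair is one score, 5 if both pairs are split, 4 if only one is (analysis sentence).
- Level: two-sided 0.05 per test (assumption).
- All targets truly null (assumption, the worst case for false positives).
- Correlation r between test statistics: not given. A range of 0 to 0.9 is used. Some correlation is likely, because all the states are self-reported in the same short assessment.

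**Step 1. At least one false positive in either direction, independent tests:** 1 − 0.95^k.

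- k = 3: 1 − 0.8574 = 14.3%
- k = 4: 1 − 0.8145 = 18.5%
- k = 5: 1 − 0.7738 = 22.6%

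**Step 2. The same with equally correlated normal test statistics**, by numerical integration of the one-factor model with critical value 1.960:

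| r | 3 targets | 5 targets |
|---|---|---|
| 0.3 | 13.6% | 20.9% |
| 0.5 | 12.5% | 18.3% |
| 0.7 | 10.9% | 14.8% |
| 0.9 | 8.4% | 10.2% |

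Simulation with mixed signs (positive affect and challenge running opposite to the other three) gives nearly the same for five targets: 20.9%, 18.3% and 14.9% at 0.3, 0.5 and 0.7.

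**Step 3. Count only apparent improvement**, since a significant worsening would not be carried forward as engagement. A single test then has 2.5%, and the independent case is 1 − 0.975^k.

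| r | 3 targets | 5 targets |
|---|---|---|
| 0 | 7.3% | 11.9% |
| 0.5 | 6.3% | 9.1% |
| 0.9 | 4.2% | 5.1% |

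**Step 4. What each remedy would do.**

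- *Label the tests exploratory and report every estimate.* The models, estimates, intervals and p-values stay the same, and so do all the percentages above.
- *Holm.* The first step tests at 0.05/k, with critical value 2.394 (k = 3) or 2.576 (k = 5). Power for a given target at that step is Φ(z_power + 1.960 − critical value). From 80%: Φ(0.842 + 1.960 − 2.394) = 66% and Φ(0.842 + 1.960 − 2.576) = 59%. From 50%: Φ(1.960 − 2.394) = 33% and Φ(1.960 − 2.576) = 27%.
- *One lead target at 0.05.* The error for that target is held at 5% with no loss of power for it, but the other targets are demoted in a study meant to learn which of them respond.

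**Step 5. Does the plan contain the rule that makes Steps 1 to 3 bite?** Those figures are the error rate of one decision: declare engagement if any target is significant. The analysis sentence sets up a separate comparison for each target, and no section says that one positive comparison establishes engagement overall. Nor does any section say that targets are kept or dropped according to significance. The statement about informing targets is attached to learning about the mechanisms that link early adversity to midlife health, not to the 15-minute comparisons. Without the any-one-counts rule, the relevant error is the per-target 5%.

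**The case for a change.** The strongest reply is that pilot status settles only whether strict family-wise control is needed, not how several primary tests will be read when they disagree. The investigator does promise tests, does use the word primary, and leaves open whether the slash pairs are split, a choice that could be made after seeing the data. A sentence or two would settle all this at no cost in data or power. And even with r = 0.9 the two-sided figure is 8.4% to 10.2%, still above 5%.

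Much of this stands as description. The count is unclear, the tests carry no label, and the arithmetic is right. What does not follow is a defect in the analysis. The wording is primary intervention target, which can be read as the states the intervention chiefly aims at rather than as confirmatory endpoints. That stressed feeling is measured but left off the list fits this reading, though it does not prove it. Whether a pair is split is a scoring matter that an analyst settles from the instrument, and because the plan compares every listed target, reporting all of them is already implied. The suggested sentences would record a policy for interpretation. They would not alter any result or lower the error rate that prompted the concern.

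**Conclusion.** The concern does not call for a change. The plan as written yields a valid estimate and test for each listed target, and the protocol leaves the confirmatory question to a later, adequately powered study. The figures of 14.3% to 22.6% depend on four things the documents do not state: a per-test level of two-sided 0.05, all targets null, independent tests, and a rule that any one significant target proves engagement. Allowing for correlation up to 0.9 lowers them to 8.4% to 10.2%. Counting only improvement, they are 7.3% to 11.9% when independent and 6.3% to 9.1% at r = 0.5, against 2.5% for one test.

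The remedies that would alter inference, Holm or a single lead target, are trade-offs on which reasonable statisticians differ in a small pilot, and neither is clearly better than separate unadjusted estimates. What is left is missing detail that an analyst fills in sensibly: settle the scoring, report every target with its interval, and read the results as the preliminary data the protocol says they are. The conclusion would change if a report claimed overall target engagement on the strength of one significant target. Nothing in the plan commits to that.
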